10.5 MISSING AND SPURIOUS DATA

All data collected under this study protocol will be included in the assessment of subject safety. Missing or incomplete AE data will assume greatest relationship to study drug and/or severity.

For the exploratory effectiveness endpoint analyses (WOMAC and PGA), missing scores will be imputed in when the worst observation carried forward to aid in the assessment of the robustness of the results.

11 REGULATORY, ETHICAL AND LEGAL OBLIGATIONS

11.1 DECLARATION OF HELSINKI

The Principal Investigator will ensure that this Study is conducted in accordance with the most recent revision of the Declaration of Helsinki.

11.2 GOOD CLINICAL PRACTICE

The Study will be conducted according to the study protocol and to Standard Operating Procedures (SOPs) that meet the guidelines provided by the International Conference on Harmonization (ICH) for Good Clinical Practice in clinical studies.

11.3 INSTITUTIONAL REVIEW BOARDS/ETHICS COMMITTEES

Before implementing this study, the protocol, the proposed subject informed consent forms and other information for the subjects, must be reviewed by a properly constituted committee or committees responsible for approving clinical studies. The IRB/IEC written, signed approval letter/form must contain approval of the designated investigator, the protocol (identifying protocol title, date and version number), and of the subject informed consent form (date, version).

Any change or addition to the protocol can only be made in a written protocol amendment that must be approved by the Sponsor, the IRB/IEC and the Health Authorities.

11.4 REGULATORY AUTHORITY APPROVAL

Before this study is implemented, the protocol must be approved by the relevant regulatory authority.

11.5 INFORMED CONSENT

The investigator must fully inform the subject of all pertinent aspects of the trial including the written information approved/favorably assessed by the IRB/IEC.

Prior to the start of the pre-study examination, the written informed consent form must be signed and personally dated by the subject and by the physician who conducted the informed consent discussion. One copy of the written information and signed consent form must be given to each subject and one copy must be retained in the investigator's study records.

11.6 SUBJECT CONFIDENTIALITY AND DISCLOSURE

Data on subjects collected on eCRFs during the trial will be documented in an anonymous fashion and the subject will only be identified by the subject number, and by his/her initials If, as an exception, it is necessary for safety or regulatory reasons to identify the subject, all parties are bound to keep this information confidential.

The investigator will guarantee that all persons involved will respect the confidentiality of any information concerning the trial subjects. All parties involved in the study will maintain strict confidentiality to assure that neither the person nor the family privacy of a subject participating

in the trial is violated. Likewise, the appropriate measures shall be taken to prevent access of non-authorized persons to the trial data.

11.7 COLLECTION, MONITORING AND AUDITING STUDY DOCUMENTATION, AND DATA STORAGE

11.7.1 Collection of Data and Monitoring Procedures

This study will use a 21 CFR Part 11 compliant electronic data capture system (eDC). An electronic case report form (eCRF) is used for data recording. All data requested on the eCRF must be entered and all missing data must be accounted for.

The data will be checked for completeness and correctness as it is entered by the real-time online checks applied by the eDC system. Off-line checks will also be run to perform any additional data review required. Discrepancy reports will be generated accordingly and transferred to the study center for resolution by the investigator or his/her designee.

Accurate and reliable data collection will be assured by verification and cross-check of the eCRF against the investigator's records by the study monitor (source document verification), and the maintenance of a study drug-dispensing log by the investigator.

Before study initiation, at a site initiation visit or at an investigator's meeting, a Sponsor representative will review the protocol and case report forms with the investigators and their staff. During the study a monitor will visit the site regularly to check the completeness of subject records, the accuracy of entries on the case report forms, the adherence to the protocol and to Good Clinical Practice, the progress of enrollment. The monitor will ensure during on-site visits that study medication is being stored, dispensed and accounted for according to specifications. Key trial personnel must be available to assist the monitors during these visits.

The investigator must give the monitor access to relevant hospital or clinical records, to confirm their consistency with the case report form entries. No information in these records about the identity of the subjects will leave the study center. Monitoring standards require full verification for the presence of informed consent, adherence to the inclusion/exclusion criteria, documentation of SAEs and the recording of primary efficacy and safety variables. Additional checks of the consistency of the source data with the eCRFs are performed according to the study-specific monitoring plan.

11.7.2 Auditing Procedure

In addition to the routine monitoring procedures the Sponsor or the regulatory authority can conduct an audit or an inspection (during the study or after its completion) to evaluate compliance with the protocol and the principles of Good Clinical Practice.

The investigator agrees that representatives of the Sponsor and Regulatory Authorities will have direct access, both during and after the course of this study, to audit and review all study-relevant medical records.

11.7.3 Retention of Documents

The investigator must maintain source documents for each subject in the study, consisting of all demographic and medical information, including laboratory data, x-ray, etc., and keep a copy

of the signed informed consent form. All information on case report forms must be traceable to these source documents in the subject's file. Data without a written or electronic record will be defined before trial start and will be recorded directly on the case report forms, which will be documented as being the source data.

11.8 DISCLOSURE OF INFORMATION

All information provided to the investigator by Ampio Pharmaceuticals, Inc. or their designee, will be kept strictly confidential. No disclosure shall be made except in accordance with a right of publication granted to the investigator.

No information about this study or its progress will be provided to anyone not involved in the study other than to Ampio Pharmaceuticals, Inc. or its authorized representatives, or in confidence to the IRB, or similar committee, except if required by law.

11.9 DISCONTINUATION OF THE STUDY

It is agreed that, for reasonable cause, either the investigator or Ampio Pharmaceuticals, Inc., may terminate the investigator's participation in this study after submission of a written notice. Ampio Pharmaceuticals, Inc., may terminate the study at any time upon immediate notice for any reason, including the Sponsor's belief that discontinuation of the study is necessary for the safety of subjects.

11.10 STUDY REPORT, PUBLICATION POLICY AND ARCHIVING OF STUDY DOCUMENTATION

11.10.1 Study Report and Publication Policy

An ICH-compliant integrated clinical and statistical report will be prepared upon completion of the study and data analysis. The results of the study will be published in a relevant peer-reviewed journal, with authorship status and ranking designated according to the acknowledged contributions of participating investigators, institutions and the Sponsor.

11.10.2 Study Documents

The investigator must maintain source documents for each subject in the study, consisting of all demographic and medical information, questionnaires, including laboratory data, x-ray, etc., and keep a copy of the signed informed consent form. All information on the e-case report forms must be traceable to these source documents in the subject's file. Data without a written or electronic record will be defined before trial start and will be recorded directly on the eCRFs, which will be documented as being the source data.

11.10.3 Archiving of Documents

Essential documents, as listed below, must be retained by the investigator for as long as needed to comply with national and international regulations. The Sponsor will notify the investigator(s)/institution(s) when the study-related records are no longer required. The investigator agrees to adhere to the document retention procedures by signing the protocol. Essential documents include:

- IRB/IEC/REB approvals for the study protocol and all amendments

- All source documents and laboratory records
- CRF copies (electronic copies on a CDROM)
- Subjects' informed consent forms (with study number and title of trial)
- FDA form 1572
- Any other pertinent study document.

2. OBJECTIVES

2.1 Primary Objective

The primary trial objective is to carry on from the AP-003-C main study (one injection) and evaluate the safety of a 4-mL intra-articular (IA) injection of Ampion with repeat dosing every 12 weeks for 52 weeks and/or with five total injections of Ampion.

2.2 Secondary Objective

The exploratory objectives are to analyze the efficacy of a 4-mL intra-articular (IA) injection of Ampion with repeat dosing every 12 weeks for 52 weeks and/or with five total injections of Ampion.

2.3 Study Design

Subjects who have completed the AP-003-C main study (n=161) will be offered the option to roll-over to the open label extension study (AP-003-C-OLE) at their final visit of the AP-003-C main study (Visit 7). Enrollment into the AP-003-C-OLE study (Visit 9) allows a 170-day screening window from the AP-003-C main study Visit 7. AP-003-C-OLE study will include the following visits:

Visit 9/Enrollment (Day-170 to Day 0, but not to occur before completion of AP-003-C main study) in-office visit, Visit 10 (24 hours after enrollment post injection follow-up telephone call), Visit 11 in-office visit (Day 84 ±14 days), Visit 12 (24 hours after Visit 11 post injection follow-up telephone call), Visit 13 in-office visit (Day 168 ± 14 days), Visit 14 (24 hours after Visit 13 post injection follow-up telephone call), Visit 15 in-office visit (Day 252 ± 14 days), Visit 16 (24 hours after visit 15 post injection follow-up telephone call), Visit 17 final in-office visit (Day 280 ± 14 days).

The safety of repeat dosing will be evaluated at all visits; in-office visit safety assessments will include vital signs, physical exams, evaluation of AEs, and laboratory analysis. Phone visits will evaluate for AEs.

The clinical effects of treatment on OA pain will be evaluated during all in-clinic visits using the Western Ontario and McMaster Universities Arthritis Index (WOMAC®) osteoarthritis Index 3.1 and the Patient's Global Assessment of disease severity (PGA). The WOMAC will also be utilized to assess the contralateral knee pain at Enrollment/Visit 9 and Visit 17 (or Early Termination Visit).

The WOMAC® is a validated pain scoring system and sets the standard for the subject response. In order not to bias the collection of data, only questions from the validated WOMAC pain scale will be asked of subjects.

2.4 Sample Size

The original AP-003-C study used total of 170 subjects (140 Ampion; 25 Saline) to test the following hypotheses.

$$H_0: \pi \leq 30\% \text{ versus } H_A: \pi > 30\%$$

This study is observational, using subjects who consent from the AP-003-C study, so no formal sample size was calculated. In following ICH E1A safety guidelines to assess clinical safety in long-term treatment of non-life-threatening conditions, it is anticipated that 100 subjects will be enrolled into this study.

3. PRIMARY STUDY ENDPOINTS

3.1 Primary Endpoint

The primary trial endpoint is to evaluate the incidence and severity of treatment-emergent adverse events (TEAEs)

3.2 Exploratory Endpoints

The exploratory endpoints in this trial will be assessed at Visit 9 (Enrollment), Visit 11 (Week 12), Visit 13 (Week 24), Visit 15 (Week 36) and Visit 17 (Week 40) and are:

- Responder status based on the OMERACT-OARSI responder criteria
- Evaluate OMERACT-OARSI 'controlled' responder defined as a 20% improvement in Pain and Function and 0.5 point absolute change in the 5-point Likert Scale
- Evaluate 20% improvement in PGA and 0.5 point absolute change in the 5-point Likert Scale
- Mean change and percent change in WOMAC A pain subscore
- Mean change and percent change in WOMAC B stiffness subscore
- Mean change and percent change in WOMAC C physical function subscore
- Mean change and percent change in PGA

- Mean Change and percent change in WOMAC A pain subscore questions 1 and 2 (pain with movement)
- Mean Change and percent change in WOMAC A pain subscore questions 3–5 (resting pain)
- Change in contralateral knee pain (WOMAC A)
- Change in contralateral knee stiffness (WOMAC B)
- Change in contralateral knee function (WOMAC C)
- Time to Total Knee Replacement (TKR)
- Use of rescue analgesia (amount of acetaminophen used)

4. HYPOTHESES AND METHODS

4.1 Primary Analysis Methodologies

Since this is an observational study on the repeat administration of Ampion 4 mL injection, no formal hypotheses will be tested in this study. There will be no comparisons made to threshold values or to “historical” control values. There is no comparator in this study.

All analyses will be descriptive in nature and will be performed at each efficacy assessment (Visit 9 (Enrollment), Visit 11 (Week 12), Visit 13 (Week 24), Visit 15 (Week 36) and Visit 17 (Week 40)). For dichotomous outcomes, the percentage of patients with that outcome will be estimated and exact 95% binomial confidence intervals will be calculated. These dichotomous outcomes are:

- The incidence of treatment emergent adverse events
- Responder status based on the OMERACT-OARSI responder criteria
- Evaluate OMERACT-OARSI ‘controlled’ responder defined as a 20% improvement in Pain and Function and 0.5 point absolute change in the 5-point Likert Scale
- Evaluate 20% improvement in PGA and 0.5 point absolute change in the 5-point Likert Scale

The outcomes with more continuous responses will be analyzed via descriptive statistics (n, mean, standard deviation, median, minimum, and maximum). Also, 95% confidence intervals from the mean response will be calculated. These outcomes are:

- Mean change and percent change in WOMAC A pain subscore
- Mean change and percent change in WOMAC B stiffness subscore
- Mean change and percent change in WOMAC C physical function subscore
- Mean change and percent change in PGA
- Mean Change and percent change in WOMAC A pain subscore questions 1 and 2 (pain with movement)
- Mean Change and percent change in WOMAC A pain subscore questions 3–5 (resting pain)
- Change in contralateral knee pain (WOMAC A)
- Change in contralateral knee stiffness (WOMAC B)
- Change in contralateral knee function (WOMAC C)

Differences in pain scores between successive visits will be estimated via descriptive statistics and confidence intervals.

The time to total knee replacement will be summarized using Kaplan-Meier methodologies. The use of rescue analgesia will be summarized as the dichotomous outcome on the number of patients using rescue medication and as continuous variables on the number of medications use.

This is an Open Label Extension study, which is designed to assess the safety of patients who have previously completed the main AP-003-C study. It is also desirable to assess the efficacy of all patients relative to their original baseline and first injection and exposure to the investigational product. Thus, the previously mentioned statistics will be calculated using the baseline from the main study, AP-003-C.

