5.1.10 Early Termination Visit

The following procedures will be performed at Early Termination Visit:

- Perform and record physical examination.
- Record vital signs. (Measure body temperature, systolic / diastolic blood pressure [BP] and pulse rate)
- Complete the WOMAC Index 3.1. for the study knee
- Complete the WOMAC Index 3.1 for the contralateral knee
- Complete the PGA for the study knee
- Record if subject was able to delay TKR by participation in study
- Record AEs if observed.
- Record concomitant medications.
- Draw safety labs
- [Obtain x-ray of study knee \(excluding subjects who terminate in order to receive TKR\)](#)
- Review/Collect rescue medication (acetaminophen [paracetamol]).

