10.3.7 Number of subjects to receive study drug

Planned enrollment is up to 161 subjects; all subjects that consent to participate in the AP-003-C-OLE study. Assuming a 15% dropout rate, a total of 136 subjects will be enrolled.

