- Change in contralateral knee pain (WOMAC A) between Visit 9 and Visit 17
- Change in contralateral knee stiffness (WOMAC B) between Visit 9 and Visit 17
- Change in contralateral knee function (WOMAC C) between Visit 9 and Visit 17
- Time to Total Knee Replacement (TKR)
- Use of rescue analgesia (amount of acetaminophen used)

Exploratory efficacy analyses include the mean change and percent change in WOMAC A, WOMAC B, WOMAC C, WOMAC A1-2, WOMAC A3-5, PGA and amount of acetaminophen used from Visit 1 to Visit 17 using an analysis of covariance model, adjusted for baseline value.

Percent responders using the OMERACT-OARSI responder criteria will be analyzed defined as the percent of subjects whom respond to treatment from Visit 1 to Visit 17. Interim visits will also be analyzed.

1. High improvement in pain or in function $\geq 50\%$ and absolute change in Likert pain scale of ≥ 1 OR
2. Improvement in at least two of the 3 following:
 - a. pain $\geq 20\%$ and absolute change in Likert score ≥ 0.5
 - b. function $\geq 20\%$ and absolute change in Likert score ≥ 0.5
 - c. subject's global assessment $\geq 20\%$ and absolute change in Likert score ≥ 0.5

All of the above endpoints will be evaluated via descriptive statistics and confidence intervals.

The WOMAC Pain Score, the WOMAC Function Score, then PGA score and the OMERACT-OARSI responder criteria, will be analyzed via a repeated measures analysis of variance to determine if there is a significant time effect for these endpoints. Also, to aid in the interpretation of these results, a stability analysis will be performed on these same endpoints. That is, mean pairwise differences between administration time points will be calculated along with their 95% confidence intervals. If stability is achieved at some time point, then the following mean differences should be not be different from zero, in that the confidence interval should include zero.

Adverse events will be tabulated for both number of subjects and number of events by subject and overall study population, summarized by any event, body system, and preferred term. Summaries by serious, severity, and relationship will also be done.

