4.7 Data presentation

4.7.1 Demographic and Baseline Characteristics:

Demographic (e.g., age, sex, race, and ethnicity) and Baseline characteristics (e.g., weight, height, prior injection of another intra-articular therapeutic for OA of the knee) will be summarized using descriptive statistics, overall and by treatment group for the ITT analysis population.

4.7.2 Medical History and Physical Examination:

The number and percent of subjects with past and current medical disorders at the time of randomization will be presented overall for the ITT analysis population. Results of any abnormalities documented from the abbreviated physical examination at Baseline and Week 40, will be summarized overall for the safety and ITT analysis populations.

4.7.3 Concomitant Medications or Treatments:

The number and percent of subjects receiving concomitant medications or treatments prior to and during the study and at the final visit will be tabulated and presented overall for the ITT analysis population. Concomitant medications/treatments will be

summarized using descriptive statistics and will be presented by type of drug (WHO DRUG classification) overall for the safety and ITT analysis populations.

4.7.4 Safety data:

Safety data will be evaluated by changes in vital sign measurements, physical exam, laboratory analysis, and the frequency and severity of AEs. Concomitant medication will be recorded for safety.

Adverse events:

The Investigator is responsible for monitoring the safety of subjects who have enrolled in the study. All AEs considered related, or possibly related to Ampion, will be followed until the event resolves or stabilized without further change. Subjects will be followed for the occurrence of AEs until 12 weeks after the first dose of study medication.

Investigators are required to document all AEs occurring during the clinical trial, commencing with the first day of treatment through the end of study. AEs should be properly documented on the appropriate CRF pages.

The severity of AEs (mild, moderate, severe), relatedness (related, possibly related, unrelated) along with the duration, action taken, and outcome (e.g., study withdrawal) will also be recorded. In addition, events meeting the criteria of a Serious Adverse Event (SAE) must be reported to the Sponsor within 24 hours on the SAE reporting forms.

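### Early Termination (Visit 18) assessments have no defined place in the analysis, and two stated rules, for examination abnormalities and for the contralateral knee, leave them out

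*SAP*

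**What the plan says.** **Collection.** Protocol 5.1.10 and Table 6.1 schedule a physical examination, study-knee WOMAC and PGA at ET, and 5.1.10 adds "Complete the WOMAC Index 3.1 for the contralateral knee". Protocol 3.1 and SAP 2.3 treat ET as the alternative to Visit 17 for the contralateral knee. Protocol Section 6 says that the study-knee examination looks for effusion and tenderness.

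**Analysis visits.** SAP 4.1 says the analyses "will be performed at each efficacy assessment (Visit 9 (Enrollment), Visit 11 (Week 12), Visit 13 (Week 24), Visit 15 (Week 36", and the list ends with Visit 17 (Week 40). SAP 3.2 and Protocol 10.3.11.5 name the same five visits. The visit table in SAP 4.2 shows Visit 18 without a day or window.

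**Contralateral knee.** Protocol 10.4.2 defines "Change in contralateral knee pain (WOMAC A) between Visit 9 and Visit 17", and treats stiffness and function in the same way. The table list in SAP Section 7 names no contralateral table.

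**Examination.** SAP 4.7.2 summarises "abnormalities documented from the abbreviated physical examination at Baseline and Week 40". Protocol 10.3.11.2 summarises any documented abnormality, with no visit limit. SAP Section 7 lists no examination table, only Listing 16.14.

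**Missing data.** SAP 4.8 imputes WOMAC A, WOMAC C and PGA in the ITT population. Worst observation carried forward is the primary method, with LOCF and multiple imputation as alternates. It does not say whether a Visit 18 score may be carried.

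**The concern.** Subjects who leave early are unlikely to be a random subset. The protocol itself foresees some leaving for knee replacement, and others will leave because of adverse events. The sites are asked to measure these subjects at exit, yet the analysis text does not say where the measurement goes.

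In a single-arm, open-label study reported descriptively, who is counted at the last visit does much to shape the message. Two things are at stake. First, the primary objective is safety, and a knee finding made at exit, or at any visit between Baseline and Week 40, is outside the one examination summary that the SAP describes. Second, two programmers working from the same SAP could produce different Week 36 and Week 40 efficacy tables, depending on what each did with Visit 18.

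**Working it through.** **1. How many subjects.** The inputs come from Protocol 10.3.7: "Planned enrollment is up to 161 subjects" and "Assuming a 15% dropout rate, a total of 136 subjects will be enrolled".
- Plan's figure: 161 × (1 − 0.15) = 136.85, truncated to 136. In reverse, 136 / 0.85 = 160. The figure reproduces, although it counts subjects remaining after dropout rather than subjects enrolled.
- Early leavers: 161 × 0.15 = 24.15, about 24.
- SAP 2.4 says "it is anticipated that 100 subjects will be enrolled into this study": 100 × 0.15 = 15.

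These are upper limits. Protocol 7.2 includes loss to follow-up and withdrawn consent, and such subjects may have no ET visit.

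**2. Where each ET item can go as written.**

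| ET item | Analysis text | Route for the ET value |
|---|---|---|
| Examination | SAP 4.7.2: Baseline, Week 40 | Listing 16.14, or an AE if reported as one |
| Contralateral WOMAC | Visit 9 to Visit 17 | None stated |
| Study-knee WOMAC A, C, PGA | Visits 9, 11, 13, 15, 17 | Carry-forward in ITT; eligibility unstated |
| Study-knee WOMAC B | Same five visits | Not named in SAP 4.8; Protocol 10.5 names WOMAC in general, for robustness |

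**3. Examination.** A completer has five examinations (Visits 9, 11, 13, 15, 17). SAP 4.7.2 uses two of them and leaves out 5 − 2 = 3. An early leaver contributes Baseline only.

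**4. Contralateral knee.** The only time points are Visit 9, Visit 17 and ET. A leaver therefore has no change score under the stated definition. If a carry-forward rule were borrowed and ET were not eligible, only the Visit 9 value could be carried, so the change would be zero by construction.

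**5. How far visit windows help.** Counting from the first extension injection:
- Visit 11: 84 ± 14 = Days 70–98 (29 days)
- Visit 13: 168 ± 14 = Days 154–182 (29 days)
- Visit 15: 252 ± 14 = Days 238–266
- Visit 17: 280 ± 14 = Days 266–294

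The last two meet at Day 266 and together span 57 days. In-window days are 29 + 29 + 57 = 115 of Days 1–294, or 39%. An ET visit on Day 250 falls in the Visit 15 window, but Visit 17 is still missing. An ET visit on Day 110 falls in no window. Window assignment alone is therefore not enough, and the carry-forward rule has to be settled too.

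**6. Direction.** Higher scores are worse. If the worst observation means the highest score so far, making ET eligible can only leave a carried value unchanged or raise it. But an in-window ET score used as observed replaces a carried worst score and may be lower. LOCF and the tables without imputation can move either way. The documents give no outcome data for leavers, so no net direction follows.

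**The case against.** The strongest reply is that silence is not exclusion. Neither SAP 4.8 nor Protocol 10.5 limits the carried observation to scheduled visits, and a poor exit score is just what a worst-observation rule would tend to select. SAP 4.2 includes Visit 18 in its visit table, and SAP 5.2 ends the study at Visit 17 unless the subject terminates early. For study-knee WOMAC A, WOMAC C and PGA in the ITT population this stands: the ET score is undefined, not barred. It does not help the per-protocol tables, for which SAP 4.8 states no imputation, or the items that SAP 4.8 does not name.

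Safety is also partly covered. SAP 4.8 takes all collected data into the safety assessment, SAP 4.7.4 evaluates physical examination without a visit limit, and AEs are recorded at ET and may be identified from the examination (Protocol 9.3). That stands too, but it leaves the narrower wording of SAP 4.7.2 in conflict with Protocol 10.3.11.2.

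The efficacy outcomes are exploratory and, in the words of SAP 4.1, "no formal hypotheses will be tested in this study". This limits the consequence, though it does not settle which values the tables should contain.

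A last objection concerns mapping. Scores at Visits 11 to 15 are taken before injection, about 84 days after the previous dose. Filing a Day 110 exit under Week 24 would mix in a score taken 110 − 84 = 26 days after a Day 84 injection. That is a sound reason not to move out-of-window ET scores to the next visit as observed values.

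**Conclusion.** The point holds as a gap in definition plus two specific omissions. Followed as written, SAP 4.7.2 leaves examination findings from Visits 11, 13, 15 and ET out of its summary, and Protocol 10.4.2 leaves every ET contralateral score out of the change endpoints. For the study knee, the handling of ET scores is undefined.

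Up to about 24 of 161 subjects, or 15 of 100, could be affected by the ET gap. This assumes that the protocol's 15% dropout applies and that every leaver attends an ET visit; fewer attending means fewer affected. The examination restriction at Visits 11, 13 and 15 touches all subjects seen at those visits.

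A reader might infer that the last status of every early leaver is discarded and that the Week 40 results are therefore too favourable by some amount. The documents do not support this. Leavers' scheduled visits are still analysed, some leavers will have no ET visit, and the worst-observation rule may already bring in the exit score or an equally poor one. Any figure for the shift would rest on assumed leaver outcomes, so neither its size nor its direction is claimed here.

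**What to change.** 1. **SAP 4.7.2:** summarise examination abnormalities at every examined visit and at last visit, defined as Visit 17 or ET. This brings it into line with Protocol 10.3.11.2.
2. **Contralateral WOMAC A, B and C:** define change from Visit 9 to Visit 17 or ET, as the data are collected, and show it with and without ET values.
3. **Study-knee WOMAC A/B/C, PGA and responder status (SAP 4.1 and 4.8):** use an ET score at the scheduled visit whose window contains it. State that observed ET scores are eligible for the worst-observation and last-observation carry-forward. Show tables with and without them. Do not assign an out-of-window ET score to the next scheduled visit as an observed value.

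Two details need a sentence each: which visit takes an ET score on Day 266, and what happens if a scheduled score already exists in the same window.

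The cost is SAP wording, a visit-mapping variable and some extra tables, with no new data. The small downside is that ET values come at varying times since injection, which is why both sets of tables should be shown.
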